### **Quality of Informed Consent:**

Understanding of chemotherapy benefits: The first primary outcome is a validated item from CANCORS. Patients are asked: “After talking with your doctors about chemotherapy, how likely did you think it was that chemo would cure your cancer?” Responses (“very likely,” “somewhat likely,” “a little likely,” “not at all likely,” “don’t know”) will be dichotomized to accurate (“not at all likely”) and inaccurate (all others). The pre-specified time-point for assessing the primary outcome is at the follow-up assessment, although patients will also be asked this question at baseline and the post-decision survey. Similar to CanCORS, patients will also be asked how likely they think it is that chemotherapy will “help you with problems or symptoms you are having because of your cancer,” “control the growth of your cancer,” and “help you live longer.” These additional items are included in the post-decision survey alone.

To assess understanding of treatment goal, patients are asked at the post-decision survey, “according to your doctor, what is the goal of the chemotherapy?” with the ability to choose any/all of the following response options: cure, control cancer growth, alleviate symptoms, prolong life, or other. Selecting either control cancer growth, and/or alleviate symptoms, and/or prolong life are defined as accurate understanding; “to cure” was inaccurate.

Understanding of chemotherapy risks: Modified items from Leighl et al will assess patients’ understanding of the potential risks (e.g. side effects) of their chemotherapy choice via participant questionnaire. These items include understanding of key risks (e.g., FOLFOX+/-bevacizumab (e.g. fatigue, nausea/vomiting and neuropathy), and FOLFIRI+/-bevacizumab (e.g. fatigue, nausea/vomiting, diarrhea, hair loss)). The accuracy of patients’ understanding of chemotherapy risks will be scored based upon the chemotherapy regimen they opted to receive, as described below:

- Patients initiating FOLFOX or FOLFOX bev will be considered to have an accurate understanding of risks if they respond that they are somewhat/very likely to experience neuropathy and nausea and a little/not very likely to experience hair loss  
We will create similar algorithms for all of the other chemotherapy regimens based upon well-established toxicity profiles.

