## 6.0 STATISTICAL ANALYSIS

We will test hypotheses that the study intervention---informed consent (IC) video/written tools developed with patient and clinician input---can improve patient-centered decision making for subjects contemplating palliative chemotherapy for advanced GI cancer.

**Objective 1:** Determine if the multi-media informed consent (IC) tools improve patients' understanding of benefits and risks of palliative chemotherapy as compared to the standard IC process.

*Hypothesis:* The multi-media IC tools will decrease the likelihood that patients overestimate the curative potential of palliative chemotherapy as compared to the usual IC process. (primary study outcome)

*Hypothesis:* The multi-media IC tools will increase the likelihood that patients understand the goal of treatment as compared to the usual IC process.

*Hypothesis:* The multi-media IC tools will increase the likelihood that patients will have an accurate understanding of the risks of chemotherapy as compared to the usual IC process.

**Objective 2:** Determine if the multi-media informed consent (IC) tools decrease decisional conflict, increase the likelihood patients achieve their preferred role in decision-making, and increase satisfaction with the chemotherapy IC process as compared with the standard IC process.

*Hypothesis:* The multi-media IC tools will decrease decisional conflict as compared to the usual IC process

*Hypothesis:* The multi-media IC tools will increase the likelihood that patients achieve their preferred role in treatment decision-making as compared to the usual IC process

*Hypothesis:* The multi-media IC tools will increase satisfaction with the chemotherapy IC process as compared to the usual IC process

**Objective 3:** Determine if the multi-media informed consent (IC) tools enhance patients' prognostic understanding, increase advance care planning, and facilitate patient-physician conversations about end-of-life care preferences.

*Hypothesis:* Patients randomized to the intervention will have more realistic expectations of their prognosis as compared to patients randomized to the usual IC process.

*Hypothesis:* Patients randomized to intervention will be more likely to have designated a healthcare proxy and more likely to have a DNR order as compared to patients randomized to the usual IC process

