*Hypothesis:* Patients randomized to the intervention will be more likely to discuss their end-of-life care preferences with their healthcare proxy, and with their oncologist as compared to patients randomized to the usual IC process.

We will adhere to standard reporting principles delineated by the CONSORT statement for conduct and reporting of randomized trials. Primary reports will reflect the as randomized, "intention to treat" principle, however, we will also describe results according to actual exposure to the study interventions (based on patients' self-report of whether they reviewed the standard-of-care, or investigational chemotherapy informed consent materials). Fisher's exact test will test the difference between the study arms in the first primary outcome (the proportion of patients at follow-up assessment who fail to understand that chemotherapy is "not at all likely" to cure their cancer, as assessed by an item from CANCORS). We will also test the influence of the intervention on secondary outcomes (e.g. understanding of the goal of palliative chemotherapy, chemotherapy risks, decisional conflict,

**Title:** Improving Informed Consent for Palliative Chemotherapy: RCT of Usual IC versus Investigational IC

**Overall PI:** [name], Dana-Farber Cancer Institute

**Dana-Farber protocol version no./date:** v17 / August 30, 2017

achievement of preferred role in decision-making, satisfaction with chemotherapy IC process, prognostic understanding, advance care planning, discussion of end-of-life care preferences, satisfaction with MD communication, satisfaction with informed consent (IC) documents, decisional regret, emotional distress) using Fisher's exact or chi-square tests for dichotomous outcomes, and t-tests or Wilcoxon tests for linear outcomes. For missing data for primary or secondary outcomes, we will employ multiple imputation under a missing at random assumption.

Subset analyses will explore the effect of the intervention on 1) patients making a decision about 1st line treatment, 2) patients making a decision about 2nd line treatment, 3) patients with colorectal cancer, and 4) patients with pancreatic cancer.

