Because the effects of our intervention may be moderated by patient characteristics (e.g. age, race/ethnicity, health literacy and numeracy, communication preferences, decisional control preferences), we plan to conduct exploratory analyses investigating whether these factors moderate the effect of the intervention on outcomes including 1) accurate understanding of chemotherapy benefits, 2) satisfaction with communication and the IC tools, 3) decisional involvement, or 4) emotional distress. For example: we hypothesize that the IC tool may lead to decreased distress among patients who prefer a detail-oriented prognostic communication style, whereas it may lead to increased distress among patients who prefer a vague and support-focused prognostic communication style. We would also hypothesize that the effects of

**Title:** Improving Informed Consent for Palliative Chemotherapy: RCT of Usual IC versus Investigational IC

**Overall PI:** [name], Dana-Farber Cancer Institute

**Dana-Farber protocol version no./date:** v17 / August 30, 2017

the intervention may be greater among patients with higher health literacy scores. We will test these hypotheses using multivariable logistic or linear regression analyses (depending upon the dependent variable), including interaction terms for collinear factors, and controlling for potential confounding factors (e.g. age, race/ethnicity, marital status).

**Power:** In the CANCORS study, 80% of mCRC patients on 1st line chemotherapy thought that chemotherapy could potentially cure their disease (median of 4 months post-diagnosis). Based on previous series and projections about our patient mix, we anticipate that 60% of patients will have inaccurate expectations about the benefits of chemotherapy. If the intervention strategy is able to better align expectations with likely outcomes by one third (33%) we will deem the intervention as having major impact. If this benchmark 33% reduction is not achieved but the intervention exposed subjects nonetheless have expectations that are more accurate, we will view the intervention as beneficial but lacking major impact. Assuming a baseline 60% rate of inaccurate expectations about the benefits of chemotherapy, with a total of 194 patients, we will have 80% power to detect a 33% decrease (20% absolute decrease) in inaccurate expectations among patients exposed to the intervention with a one-sided type I error of 2.5%.

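### The treatment-goal item allows several answers, but its scoring rule gives a response of cure plus a palliative goal both codes, accurate and inaccurate, and states no precedence

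*Combined protocol and SAP*

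**What the plan says.** Section 5.4 (Quality of Informed Consent) introduces the item with "To assess understanding of treatment goal, patients are asked at the post-decision survey". Patients are asked what their doctor said the goal of the chemotherapy was, "with the ability to choose any/all of the following response options: cure, control cancer growth, alleviate symptoms, prolong life, or other". The scoring sentence follows: "Selecting either control cancer growth, and/or alleviate symptoms, and/or prolong life are defined as accurate understanding; “to cure” was inaccurate".

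Section 6.0 makes this a named hypothesis under Objective 1: "The multi-media IC tools will increase the likelihood that patients understand the goal of treatment as compared to the usual IC process". It lists "understanding of the goal of palliative chemotherapy" among the secondary outcomes. Secondary outcomes of this kind are compared by Fisher's "exact or chi-square tests for dichotomous outcomes", so each patient needs one yes/no code.

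The primary item, in the same part of Section 5.4, takes a single answer and its rule is complete: one response is accurate and all the others are inaccurate.

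**The concern.** The scoring sentence makes two statements, and a multiple-response item can satisfy both. Someone who ticks cure and prolonged life is accurate by the first statement and inaccurate by the second. No precedence is given in Section 5.4, in Section 6.0, or anywhere else in the available text. A response of 'other' alone meets neither statement.

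The two ways of closing the gap differ in substance:

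- **Strict coding:** any tick of cure makes the response inaccurate.
- **Lenient coding:** any palliative tick makes it accurate, even beside cure. This runs against the trial's rationale (Section 1.2) and its materials (Section 5.3), which say that chemotherapy does not cure these cancers.

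If many patients tick cure together with another goal, the two codings can give quite different arm comparisons for the same data.

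**Working it through.** **1. The plan's own figure.** Section 6.0 states: "with a total of 194 patients, we will have 80% power to detect a 33% decrease (20% absolute decrease) in inaccurate expectations". The control rate comes from "Assuming a baseline 60% rate of inaccurate expectations about the benefits of chemotherapy", and the test level is one-sided 2.5%. The standard two-proportion formula without continuity correction, with mean proportion 0.5, gives

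n per arm = [1.960 × √(2 × 0.5 × 0.5) + 0.842 × √(0.6 × 0.4 + 0.4 × 0.6)]² / 0.20² = (1.386 + 0.583)² / 0.04 ≈ 96.9, so 97 per arm and 194 in total.

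The figure reproduces. It belongs to the primary outcome and does not depend on how the goal item is scored. The plan gives no power figure for the goal item.

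**2. Response patterns.** Leaving 'other' aside, four boxes give 2⁴ = 16 patterns.

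| Pattern | Number | Code under the written rule |
|---|---|---|
| At least one palliative goal, no cure | 7 | accurate |
| Cure alone | 1 | inaccurate |
| Cure plus at least one palliative goal | 7 | both |
| None of the four ('other' alone, or blank) | 1 | neither |

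So 7 of the 15 non-empty patterns receive both codes. This counts patterns, not patients; the documents give no frequencies.

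**3. What the choice could do.** Let c be the share of an arm that ticks cure, and s the share of those who also tick a palliative goal (the overlap). Suppose everyone who does not tick cure ticks a palliative goal. Then

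- strict: proportion accurate = 1 − c
- lenient: proportion accurate = 1 − c(1 − s)

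Assumptions, none of them from the documents: c = 40% (usual) v 25% (investigational), the same s in both arms, and 97 per arm all answering. Power is exact for Fisher's test at one-sided 2.5%. That level is borrowed from the primary power statement, since Section 6.0 sets none for secondary outcomes.

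| Coding | Overlap s | Accurate, usual v investigational | Difference | Power |
|---|---|---|---|---|
| Strict | any | 60% v 75% | 15 points | 55.3% |
| Lenient | 10% | 64% v 77.5% | 13.5 points | 48.7% |
| Lenient | 20% | 68% v 80% | 12 points | 42.0% |
| Lenient | 50% | 80% v 87.5% | 7.5 points | 23.5% |
| Lenient | 80% | 92% v 95% | 3 points | 7.9% |

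Worked line, s = 50%: usual 1 − 0.40 × 0.50 = 0.80; investigational 1 − 0.25 × 0.50 = 0.875.

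With c = 60% v 40%, strict coding gives 20 points and 76.4% power. Lenient coding gives 16 points and 56.5% at 20% overlap, 10 points and 30.7% at 50%, and 4 points and 10.1% at 80%. These rates copy the primary outcome's planning values, which concern a different question asked at a different time, so they are only a second illustration.

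**4. Unequal overlap.** The direction can also change. Suppose cure alone is ticked by 10% v 5%, and cure plus a palliative goal by 20% v 30%. Lenient coding gives 87/97 v 92/97 (+5.2 points, two-sided Fisher p = 0.28). Strict coding gives 68/97 v 63/97 (−5.2 points, p = 0.54). Neither is significant, but the signs differ.

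**The case against.** The strongest reply is that the intended rule is clear enough. The list of accurate answers joins the three palliative goals with and/or wording, so the authors did foresee multiple ticks. Cure is left off that list and called inaccurate in the same sentence. Given the strict scoring of the primary item and the content of the tools, letting cure override is the more natural reading. That stands, and it means a reader should not infer that the rule treats all answers as mutually exclusive, or that the two codings have equal support. It does not remove the gap: precedence is unstated, and the first clause taken literally gives the opposite code.

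Other stronger readings also fail:

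- *That a cure tick shows the patient expects cure.* The item asks what the doctor said the goal was. The patient's own expectation of cure is the primary item, whose scoring is complete.
- *That the coding would be chosen after arm-level results are seen.* Allocation is open, but the documents do not say when coding is fixed. The survey forms (Appendices E and F) are listed but not in the available text.
- *That the choice will make or remove an effect.* This appears only at high overlap. At 10% the codings nearly agree.
- *That 'other' alone must be inaccurate.* The plan does not say what 'other' captures; it might hold a valid non-curative goal.

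Reach is limited too. This is one of about a dozen secondary outcomes, and its hypothesis is in Section 6.0 but not in Section 2.0.

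**Conclusion.** The concern holds as a contradiction in one scoring rule: a response of cure plus a palliative goal is both accurate and inaccurate, and no precedence is stated. It touches one secondary outcome. The primary outcome and the total of 194 stand unchanged.

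Its practical size cannot be known from the documents, because they give no rate of mixed responses. In the first assumed scenario, the lenient coding costs 1.5 points of difference at 10% overlap (15 − 13.5) and 12 points at 80% (15 − 3), with power falling from 55.3% under strict coding to 48.7% and 7.9%. Confidence is high on the wording gap and low on how much it would matter in the data.

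**What to change.** Before analysis, replace the scoring sentence in Section 5.4 with a rule that gives every such response one code: *a response is accurate if at least one of the three palliative options is selected and cure is not; any response that includes cure is inaccurate*. Report the cure-plus-palliative group separately by arm, so that readers can see how much depends on it. Decide how 'other' alone is handled in advance and without sight of arm, for example from its free text if that is collected.

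The cost is a sentence or two and one extra descriptive row, with no new data. The downside is that the proportion called accurate will be lower than under the lenient reading.

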#### **hPatient Satisfaction**

**Satisfaction with informed consent (IC) materials:** Patients will rate their satisfaction with the IC documents (standard IC document and teaching sheets for patients randomized to UIC, or study IC documents). Patients randomized to investigational IC will also complete an assessment of the acceptability of the multimedia IC tool. Patients will self-report whether or not they read the booklet or watched the video, and how many times they reviewed it.

**Satisfaction with patient-MD relationship** will be assessed by 8-items from the Human Connection Scale, which has been validated by its associations with patient quality of life, mood, and prospective association with end-of-life care patterns.

**Satisfaction with the chemotherapy decision-making process** will be assessed via five items from the Patient Assessment of Cancer Communication Experiences assessed in the post-decision survey (e.g. "I got clear, understandable information about the treatments we were considering," "I got consistent information from all my doctors and nurses; everyone was on the same page;" "My doctors and nurses helped me cope with the uncertainty or unknowns about my treatment decisions;" "I got a clear recommendation about what treatment approach would be best for me;" "I was encouraged to ask questions about my treatment choices;" "I felt my doctor understood what was important to me, and considered that in recommending a treatment"), with response options with 6 response options of never, sometimes, usually, always, or does not apply. Scores for these 6 items will be summed and averaged, creating a score of 1 to 4, with 4 being the most satisfied.

#### **iCommunication**

**Patient-Centered Communication:** the Patient Assessment of Cancer Communication Experiences developed by Mazor and Arora will assess patients' perceptions of patient-centered communication at the time of 1) cancer treatment decision-making, and 2) chemotherapy treatment. At the post-decision assessment, 9 items will assess patient-centered communication regarding treatment decision-making. At the follow-up assessment, 11 different items will assess patient-centered communication while on active chemotherapy treatment.

**Prognostic communication:** At the follow-up assessment, patients will be surveyed regarding prognostic conversations they may have had with their oncologist, including whether their oncologist has discussed their life expectancy and who brought up the conversation.

**jPrognostic Understanding, care preferences and advance care planning:** Patients will be asked about their understanding of the typical life expectancy of patients' with their type of cancer. Using a single item adapted from CanCORS, patients will be asked to estimate their own life expectancy. They will also be asked about their preference for comfort-oriented versus intensive end-of-life care using an item from SUPPORT. Patients will be asked whether they have designated a healthcare proxy, and whether they have discussed with their proxy their preferences for care should they become more seriously or terminally ill. Patients will also be asked whether they have discussed with their physician

**Title:** Improving Informed Consent for Palliative Chemotherapy: RCT of Usual IC versus Investigational IC

**Overall PI:** [name], Dana-Farber Cancer Institute

**Dana-Farber protocol version no./date:** v17 / August 30, 2017

their preferences for care should they become more seriously ill, or terminally ill. Chart abstraction will determine whether the patient has completed a DNR order.

Participants will be asked questions about prognosis regardless of whether or not they skip the life expectancy sections in the booklet and video.

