## 2.0 OBJECTIVES

**Objective 1:** Determine if the multi-media informed consent (IC) tools improve patients' understanding of benefits and risks of palliative chemotherapy as compared to the standard IC process.

*Hypothesis:* The multi-media IC tools will decrease the likelihood that patients overestimate the curative potential of palliative chemotherapy as compared to the usual IC process.

*Hypothesis:* The multi-media IC tools will increase the likelihood that patients will have an accurate understanding of the risks of chemotherapy as compared to the usual IC process.

**Objective 2:** Determine if the multi-media informed consent (IC) tools enhance patients' prognostic understanding, increase advance care planning, and facilitate patient-physician conversations about end-of-life care preferences.

*Hypothesis:* Patients randomized to the intervention will have more realistic expectations of their prognosis as compared to patients randomized to the usual IC process.

*Hypothesis:* Patients randomized to intervention will be more likely to have designated a healthcare proxy and more likely to have a DNR order as compared to patients randomized to the usual IC process

*Hypothesis:* Patients randomized to the intervention will be more likely to discuss their end-of-life care preferences with their healthcare proxy, and with their oncologist as compared to patients randomized to the usual IC process.

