#### **Instrument 1: Baseline Assessment (See Appendix C)**

The baseline assessment will assess socio-demographics, information/communication preferences, decision control preferences, and illness understanding. Patients will complete this assessment after consenting for the study, but before randomization. The baseline assessment takes approximately 5 minutes to complete.

**Title:** Improving Informed Consent for Palliative Chemotherapy: RCT of Usual IC versus Investigational IC

**Overall PI:** [name], Dana-Farber Cancer Institute

**Dana-Farber protocol version no./date:** v17 / August 30, 2017

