## 5.4 Data Collection

### Summary of measures used at each patient assessment

Domain	Measures	Baseline Assessment	Post-Decision Assessment	Follow-up Assessment
Socio-demographics a	Standard assessments	• x		
Health Literacy and numeracy b	Stagliano  (2013), Lipkus  (2001)	• x		
QOL c	FACT-G 	•	•	•
Optimism d	Life Orientation Test-Revised 	•		
Distress e	Emotional wellbeing component of FACT-G 	•	•	•
Communication & decision preferences f	Control Preferences Scale 	•		
	Preferred information for chemotherapy decision (for study)	• x		
	Prognostic communication preferences, Meropol 	• x		
Illness understanding	Developed for study	• x		
Use of IC booklet and video	Video use monitored via password protected website, booklet use monitored by survey		•	• x
Quality of Informed Consentg				
Core Understanding				
Chemotherapy risks	Modified from Leighl et al 		•	
Chemotherapy benefits	Adapted from CANCORS  (primary outcome)		•	• x
Decision Making				

**Title:** Improving Informed Consent for Palliative Chemotherapy: RCT of Usual IC versus Investigational IC

**Overall PI:** [name], Dana-Farber Cancer Institute

**Dana-Farber protocol version no./date:** v17 / August 30, 2017

Adequate information	Developed for study			
Decisional involvement	Modified Control Preferences Scale 		•	
Decisional conflict	Modified SURE assessment 		•	
Satisfactionh				
MD-patient relationship	Revised Human Connection Scale 		• x	
With study IC tools/ standard IC	Developed for study		•	
With decision	Brehaut decisional regret scale 			•
Doctor-patient communicationi				
Patient-centered communication	Aurora and Mazor 		•	• x
Prognostic communication	Developed for study			• x
Prognostic Understanding j	Adapted from CANCORS 			• x
Advance Care Planning	Chart abstraction (DNR) and patient report (healthcare proxy)			• x

• Patient Participant Assessment

x Caregiver Participant Assessment

**Clinical characteristics:** Date of diagnosis (or metastatic recurrence), location of metastases, prior adjuvant chemotherapy, and ECOG performance status via chart review.

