  - B. For patients NOT making a new chemotherapy treatment decision at the time of study enrollment (e.g. they are receiving ongoing treatment with first-line palliative chemotherapy), randomization will occur at the point at which the patient is faced with a new chemotherapy treatment decision (e.g. for cancer progression, or unacceptable treatment-related toxicity). After the patient's oncologist confirms that the patient is faced with a new chemotherapy treatment decision, the study team will then randomize the patient to either the Usual IC Arm or the Investigational IC Arm of the study.

**Title:** Improving Informed Consent for Palliative Chemotherapy: RCT of Usual IC versus Investigational IC

**Overall PI:** [name], Dana-Farber Cancer Institute

**Dana-Farber protocol version no./date:** v17 / August 30, 2017

Participants will be randomized 1:1 without blinding to receive either Usual Informed Consent or Investigational Informed Consent by utilizing a randomization algorithm managed by REDCap. This will be stratified according to whether the patient is 1st line palliative chemotherapy or 2nd line palliative chemotherapy.

5. **ADMINISTER INTERVENTION:** For patients randomized to the intervention, the research assistant or the patient's oncologist or primary nurse practitioner (depending upon oncologist preference) will give the participant the relevant interventional informed consent (IC) materials.

The treating oncologist will identify which chemotherapy regimen(s) are being considered, in order to select the appropriate IC tool(s) to give the patient. Although we anticipate that most oncologists will recommend a single treatment option and will request that patients be given a single IC video and companion booklet, patients may be given both IC tools if the oncologist has recommended consideration of either FOLFOX(+/-bevacizumab), FOLFIRI(+/-bevacizumab), FOLFIRINOX, Gemcitabine + nab-paclitaxel, or Gemcitabine.

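### Proxy, DNR and end-of-life-discussion outcomes are undated and have no listed baseline value, so planning done before randomization dilutes a comparison that is otherwise valid

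*Combined protocol and SAP*

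**What the plan says.** The hypothesis in section 2.0, repeated in section 6.0, is a statement about the two arms: "Patients randomized to intervention will be more likely to have designated a healthcare proxy and more likely to have a DNR order" than usual-consent patients. A companion hypothesis covers discussing end-of-life preferences with the proxy and with the oncologist. The parent objective is to increase advance care planning and to facilitate these conversations.

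The measures table in 5.4 gives the source as "Chart abstraction (DNR) and patient report (healthcare proxy") and marks that row at follow-up only. The text of 5.4 describes the patient items: "Patients will be asked whether they have designated a healthcare proxy, and whether they have discussed with their proxy their preferences for care". The item on discussion with the physician and the DNR item also ask about current status. None of them is limited to the period since enrolment or randomization.

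For the baseline survey, 5.2 states: "The baseline assessment will assess socio-demographics, information/communication preferences, decision control preferences, and illness understanding". Section 5.7 places chart documentation of advance care planning in the follow-up abstraction, not the baseline one. Section 6.0 analyses as randomized and tests dichotomous secondary outcomes with Fisher's exact or chi-square tests, with no baseline term.

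**The concern.** The objective is about change, but the outcome is status. A patient who named a proxy, held these talks or had a DNR order before allocation counts as a success in whichever arm they enter, although the tools played no part.

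This is a realistic possibility here. Section 3.0 admits patients deciding on 2nd-line treatment and patients already on 1st-line treatment, and section 4.0 randomizes the latter only at their next treatment decision. Both groups have had time to plan.

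Three things are at stake: power to detect a real effect on new planning, the ability to see and correct a chance imbalance in prior planning, and an estimate of new planning itself. If prior planning is common, a null result on these outcomes would be hard to interpret.

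**Working it through.** **The plan's own figure.** Section 6.0 states: "Assuming a baseline 60% rate of inaccurate expectations about the benefits of chemotherapy", and "with a total of 194 patients, we will have 80% power to detect a 33% decrease (20% absolute decrease"), "with a one-sided type I error of 2.5"%. The formula is power = Φ{[d√n − 1.96√(2p̄(1−p̄))] / √(p₀(1−p₀) + p₁(1−p₁))}. With n = 97 per arm, p₀ = 0.60 and p₁ = 0.40 it gives 80.03%, so 194 patients reproduces. That calculation concerns the curability item. No power is stated for the advance-care-planning outcomes, so 97 per arm is carried over here only as a working size.

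**Model for an undated status outcome.** Let b be the share with the planning already done at randomization, equal in expectation in the two arms. Let c₀ and c₁ be the rates of new planning among the rest. Then:

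- p₀ = b + (1−b)c₀ and p₁ = b + (1−b)c₁
- p₁ − p₀ = (1−b)(c₁ − c₀)

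**Inputs.** The documents give neither b nor c. Assumed, for proxy designation only: c₀ = 20%, c₁ = 40%, two-sided 5%, and b from 30% to 70%. A proxy named before randomization is taken to remain in place.

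**Worked case, b = 50%.** p₀ = 0.5 + 0.5 × 0.2 = 60% and p₁ = 0.5 + 0.5 × 0.4 = 70%. The numerator is 0.10 × √97 − 1.96 × √(2 × 0.65 × 0.35) = 0.985 − 1.322 = −0.337. The denominator is √(0.24 + 0.21) = 0.671. Power = Φ(−0.50) = 31%.

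| b | Status rates | Difference | Power, unadjusted | Power, stratified by baseline status |
|---|---|---|---|---|
| 0% | 20% v 40% | 20 points | 87% | 87% |
| 30% | 44% v 58% | 14 points | 50% | 72% |
| 50% | 60% v 70% | 10 points | 31% | 58% |
| 70% | 76% v 82% | 6 points | 17% | 38% |

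The last column follows because patients with a proxy at baseline all score yes in both arms, so their stratum adds no information and no noise. The stratified test therefore has the power of 20% v 40% in 97(1−b) patients per arm (67.9, 48.5 and 29.1). A simulated stratified (Mantel-Haenszel) test on all randomized patients agrees.

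**Sensitivity to the assumed effect, at b = 40%.** Unadjusted power is 39% for 10% v 30%, 39% for 20% v 40% and 41% for 30% v 50%. Among those without a proxy at baseline it is 78%, 66% and 60%.

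**Is the comparison biased?** No. With no effect (c₀ = c₁ = 20%) and b = 20%, 50% or 80%, 20,000 simulated trials per setting gave a mean arm difference between −0.0001 and 0.0006 and a two-sided Fisher type I error of 3.2% to 3.5%.

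**Chance imbalance.** At b = 50% the standard deviation of the arm difference in prior planning is √(2 × 0.5 × 0.5 / 97) = 7.2 points. By the normal approximation, a gap of 10 points or more in either direction arises in about 16% of trials. That is as large as the whole 60% v 70% effect, and it could be neither seen nor adjusted for.

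**The case against.** A reader might infer that the trial cannot show whether the tools increase planning. The documents do not support that. Allocation is random ("Participants will be randomized 1:1 without blinding to receive either Usual Informed Consent or Investigational Informed Consent"), the hypotheses are worded as a comparison between arms, and section 6.0 analyses as randomized. A higher rate in the intervention arm would be valid evidence of an increase. Stratification by line of chemotherapy also limits imbalance in one likely driver of prior planning.

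A reader might also infer that no baseline value exists. That too goes further than the text. The baseline list in 5.2 is incomplete: it omits FACT-G, optimism, and literacy and numeracy, all marked at baseline in the table. The table is incomplete as well: 5.4 says the cure item is asked at baseline, yet its row carries no baseline mark. The survey and abstraction forms (Appendices C, G, I and K) are not in the text, so exact wording, reference periods and date fields cannot be seen.

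Further points stand. DNR status comes from the chart, so earlier orders may be identifiable if entries are dated; this would not rescue the patient-reported discussion items. Discussions can recur, so counting only first-ever talks would miss those the tools prompt. These are secondary outcomes without a stated power.

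Finally, making a baseline-defined subset the main analysis would carry its own risk. Section 5.5 lets some patients complete the baseline survey up to two weeks after randomization, and section 4.0 lets it be marked missing. In an unblinded trial, late answers could be affected by the allocation.

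**Conclusion.** The point stands as one of efficiency and interpretation, not validity. As described, these outcomes mix planning done before randomization with planning done after it, and the planned tests cannot separate the two. The loss in risk difference, the factor (1−b), is exact under the model. The loss in power is illustrative: under the assumed 20% v 40%, unadjusted power is about 50%, 31% and 17% at b = 30%, 50% and 70%, against about 72%, 58% and 38% with stratification.

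Even the stratified analysis stays below 80% in these three scenarios, so it improves these outcomes without making them well powered. The figures apply to proxy designation only; no size is offered for DNR orders or discussions. The conclusion also depends on the unseen forms containing no baseline item, reference period or event date.

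**What to change.** - **Baseline survey:** add three yes/no items: proxy named, preferences discussed with the proxy, preferences discussed with the oncologist. They should be answered before allocation. Patients enrolled during 1st-line treatment should be asked again at the new decision, before they are randomized. Answers from surveys completed after randomization under 5.5 should not be used as baseline values.
- **Chart abstraction:** record the date of any DNR order or proxy form.
- **Follow-up survey:** ask about discussions since the treatment decision, because talks can recur.
- **Section 6.0:** make the main analysis of these outcomes the full as-randomized comparison, stratified by or adjusted for baseline status. Report new events among patients without the event at baseline as supportive.

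The cost is three items on a survey of about five minutes, two date fields, a reference period on the follow-up discussion items and a short addition to 6.0. The downside is that the baseline survey becomes slightly longer, raises sensitive topics, and may itself prompt planning in both arms. If the forms already hold these items or dates, only the change to 6.0 is needed.
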